18 APPENDICES

18.1 PHARMACOKINETIC ASSESSMENT TIME POINTS

Detailed collection of schedules for blood (Table 13) and urine (Table 14) samples for PK analysis are presented below.

Table 13: Pharmacokinetic Time Points

Study Day	Protocol Time (hh:mm)	PK Blood
Day 1, Month 12 (Day 361 ±7 days) and Month 24	Predose (within 60 minutes before dosing)	X
(Day 721 ±7 days) ^a	00:30 (±2-min)	X
	02:00 (±5-min)	X
	04:00 (±30 min)	X
	08:00 (±30-min)	X
Day 2, Month 12 (Day 362 ±7 days) and Month 24 (Day 722 ±7 days) ^a	24:00 (±2 hours)	X

a Month 24 assessment to be performed in a subset of patients who opt to participate.

Table 14: Urine Pharmacokinetic Time Points

Study Day	Protocol Time (hh:mm), Pooled Urine	
Month 24 (Day 721 7 days)	Postdose, 0:00 to 06:00 (±30 min) ^a	
Month 24 (Day 721 ±7 days)	06:00 (±30 min) to 12:00 (±30 min)	
Month 24 (Day 721 to Day 722 ±7 days)	12:00 (±30 min) to 24:00 (±2 hours)	

Note: To be performed in a subset of patients who opt to participate. Urine volume will be recorded for each urine collection interval.

a Patients must empty bladder before this urine collection interval.

Protocol Time Study Day ADA (hh:mm) Day of dose Predose (within 240 minutes X re-start before dosing) Predose (within 240 minutes PR Month 6 X before dosing) Predose (within 240 minutes X PR Month 12 before dosing) Predose (within 240 minutes PR Month 24 X^{a} before dosing) Predose (within 240 minutes PR Month 36 X^a before dosing)

Table 15: ADA timepoints in all patients at 50 mg Q2M dose

a ADA samples collected at PR Months 24 and 36 will only be analyzed if the preceding sample was ADA positive.

Study Day	Protocol Time (hh:mm)	ADA
Day of new dose	Predose (within 240 minutes before dosing)	X
PR Month 6	Predose (within 240 minutes before dosing)	X
PR Month 12	Predose (within 240 minutes before dosing)	X
PR Month 24	Predose (within 240 minutes before dosing)	Xa
PR Month 36	Predose (within 240 minutes before dosing)	Xa

a ADA samples collected at PR Months 24 and 36 will only be analyzed if the preceding sample was ADA positive.

18.2 PERIOPERATIVE SCHEDULE OF ASSESSMENTS

18.2.1 Definitions of Minor and Major Surgery

Minor surgery is defined as any invasive operative procedure in which only skin, mucous membranes, or superficial connective tissue is manipulated and does not meet the criteria for major surgery (eg, dental extraction of <3 non-molar teeth). Minor surgical procedures may be performed at a local health care provider institution.

Major surgery is defined as any invasive operative procedure that requires any of the following:

- Opening into a major body cavity (eg, abdomen, thorax, skull)
- Operation on a joint
- Removal of an organ
- Dental extraction of any molar teeth or ≥ 3 non-molar teeth or any tooth implantation
- Operative alteration of normal anatomy
- Crossing of a mesenchymal barrier (eg, pleura, peritoneum, dura)

18.2.2 Perioperative Assessments of Safety and Hemostatic Efficacy in Patients Undergoing Major Operative Procedures

In patients who undergo a major operative procedure while on study, questionnaires will be provided to capture the exploratory perioperative assessments of hemostasis. The questionnaires may be completed by the dentist/surgeon/anesthesiologist involved in the procedure, or by the Investigator in consultation with the involved dentist/surgeon/anesthesiologist. The questionnaires include the Hemostatic Efficacy Rating Scale for Major Operative Procedures (Table 17), based on the ISTH SSC definitions (18).

Table 17: Hemostatic Efficacy Rating Scale for Major Operative Procedures

Excellent	Intra-operative and post-operative blood loss similar (approximately within 10%) to the non-hemophilic patient	
	No extra (unplanned) doses of FVIII/FIX/BPAs needed AND	
	Blood component transfusions required are similar to non-hemophilic patient	
Good	Intra-operative and/or post-operative blood loss slightly increased over expectation for the non-hemophilic patient (approximately between 10-25% of expected), but the difference is not clinically significant	
	No extra (unplanned) doses of FVIII/FIX/BPAs needed AND	
	Blood component transfusions required are similar to the non-hemophilic patient	
Moderate	Intra-operative and/or post-operative blood loss increased over expectation (approximately 25-50%) for the non-hemophilic patient and additional treatment is needed	
	Extra (unplanned) dose of FVIII/FIX/BPAs needed OR	
	 Increased blood component (within 2-fold) of the anticipated transfusion 	
None	Significant intra-operative and/or post-operative blood loss that is substantially increased over expectation (approximately >50%) for the non-hemophilic patient, requires intervention, and is not explained by a surgical/medical issue other than hemophilia	
	 Unexpected hypotension or unexpected transfer to intensive care unit (ICU) due to bleeding OR 	
	 Substantially increased blood component (approximately >2 fold) of the anticipated transfusion requirement 	

See Section 8.4 for further details regarding major operative procedures while on study. The Perioperative Schedule of Assessments in patients undergoing major operative procedures while on study is presented in Table 4.

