If the need for emergency or urgent major surgery arises during the trial, the patient should be managed medically according to the guidelines above. If an fitusiran dose is scheduled to occur on or in close proximity to the day of surgery, or anytime during the perioperative period, the dose should be withheld. The Perioperative Evaluation Period is defined as the day of the surgery through the final day on which supplemental hemostatic or antithrombotic treatments are administered as part of the perioperative treatment plan. Fitusiran dosing may be resumed at the next scheduled visit following the Perioperative Evaluation Period at the discretion of the Investigator. If multiple consecutive doses of fitusiran are withheld, the Investigator will consult with the study Medical Monitor, who will determine if the patient may continue on study.

Perioperative assessments will be performed in patients undergoing major surgery during the study as described in Section 8.4, and as scheduled in Table 4.

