Hemostatic response will be assessed at the end of the procedure (SDay 0), 24 hours postoperatively (SDay 1), and up to 14 days postoperatively (SDay 2-14; day to be determined by the Investigator) using the hemostatic efficacy rating scale (Table 17). A final postoperative visit will occur on SDay 28 (up to + 28 days) to document the date/time when perioperative hemostatic and thromboprophylaxis (if applicable) treatment was completed. The perioperative hemostatic rating will be collected via questionnaires that will be provided. The total number of patients in each rating category of hemostatic response ("none," "moderate," "good," and "excellent") will be summarized for both the intraoperative and postoperative assessments.

The end of the Perioperative Evaluation Period for each patient will be defined as the date/time when perioperative hemostatic treatment and thromboprophylaxis (if applicable) was completed, as documented at the last postoperative visit.

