- c. Missing two consecutive doses in LTE14762 (eg, a participant skips at least two consecutive scheduled doses): If participant under Q2M regimen before the dose interruption, then exclude events occurring on dates starting from the date of the last dose before the dose interruption + 57 days to the date of the dose resumption + 56 days. If participant under QM regimen before the dose interruption, then excluded events from the date of the last dose before the dose interruption + 29 days to the date of the dose resumption + 28 days. The missing two consecutive doses will be considered separately before and after the dose pause in 2020.
- d. Fitusiran treatment discontinuation in LTE14762: Exclude events occurring on any dates starting from the date of the last dose +29 days if the last dose regimen is QM (ie, until the end of the study.) If the last dose regimen is Q2M, then the start date of this intercurrent event should be last dose + 57 days.

II. Perioperative period of major surgery and major trauma is defined as the day of the surgery or trauma through the final day on which supplemental hemostatic or antithrombotic treatments are administered as part of the perioperative treatment plan.

III. Perioperative period of minor surgery is defined as the perioperative period of surgery as defined for major surgery (see above) or to 72 hours from the end of surgery, whichever is later.

IV. Period of antithrombin treatment defined as the first day of antithrombin treatment through the final day on which antithrombin or other anticoagulant therapies are administered +5 half-lives.

V. After treatment with emicizumab.

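### SAP 6.3 sets a 72-hour minimum exclusion window after minor surgery but none after major surgery, so an early post-procedure bleed can count in the primary ABR after the larger procedure and be removed after the smaller one

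*Protocol*

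**What the plan says.** SAP 6.3 removes the time covered by listed intercurrent events from every analysis period of the primary, on-treatment efficacy analysis. Two of the events concern surgery.

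- **Event II, major surgery and major trauma.** The window is "the day of the surgery or trauma through the final day on which supplemental hemostatic or antithrombotic treatments are administered" under the perioperative treatment plan. No minimum length is given.
- **Event III, minor surgery.** The window is the "perioperative period of surgery as defined for major surgery (see above) or to 72 hours from the end of surgery, whichever is later".

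Protocol 18.2.1 supplies the split. Major surgery includes "Dental extraction of any molar teeth or ≥ 3 non-molar teeth or any tooth implantation". Minor surgery covers skin, mucosa or superficial tissue and "does not meet the criteria for major surgery (eg, dental extraction of <3 non-molar teeth".

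Only bleeds treated with factor or bypassing agent (BPA) enter the primary bleeding analysis. SAP 6.3.1.1 also plans a treatment-policy ABR that keeps surgery periods in.

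**The concern.** Event III is built as the later of the event II window and a 72-hour limit. For the same duration of supplemental treatment, the minor-surgery window is therefore never shorter than the major-surgery window and can be longer. The exclusions exist to keep bleeding caused by something else, here surgery, out of the estimate. Guaranteeing that protection only for the class with the lesser tissue injury runs against this purpose, and the SAP gives no reason for it.

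Two gaps sit beside the asymmetry. If no supplemental treatment is given after a major procedure, event II has no defined end, while event III still gives 72 hours. The SAP also does not say whether factor or BPA given for a post-procedure bleed is itself part of the perioperative plan. If it is, that dose extends the window over the bleed.

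At stake are the primary on-treatment ABR, its 6-monthly summaries after restart, and the on-treatment bleed-free duration. In these, the major or minor label can decide whether a bleed counts. With at most 48 participants, tables split by hemophilia and inhibitor type, and by-year models allowed in groups as small as 3, a single bleed can be visible.

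**Working it through.** The plan states no figure on this point, so there is nothing to reproduce. The check applies the two definitions to one bleed and then sizes the effect.

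**1. Is a minimum supplied elsewhere?** Protocol 5.7 uses the same end rule as event II: "The Perioperative Evaluation Period is defined as the day of the surgery through the final day on which supplemental hemostatic or antithrombotic treatments" are given. Protocol 8.4 ends the period when hemostatic treatment and any thromboprophylaxis are complete. Neither sets a minimum. The 72-hour rule in SAP 6.3 for merging bleeds runs from an injection that treated a bleed, or from an untreated bleed, not from surgery. It does not fill the gap.

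**2. Windows.** Assume surgery ends at noon on Day 0, and let L be the last calendar day of planned supplemental treatment.

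- Major window end, in hours after surgery = 24 × (L + 1) − 12
- Minor window end = the larger of that value and 72

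Take a treated bleed 48 hours after surgery (Day 2), whose treating dose lies outside the plan.

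| Last planned treatment | Major window ends | Bleed after major | Minor window ends | Bleed after minor |
|---|---|---|---|---|
| None | undefined | undefined | 72 h | excluded |
| Day 0 | 12 h | counted | 72 h | excluded |
| Day 1 | 36 h | counted | 72 h | excluded |
| Day 2 | 60 h | excluded | 72 h | excluded |
| Day 3 | 84 h | excluded | 84 h | excluded |
| Day 5 | 132 h | excluded | 132 h | excluded |

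The two classes diverge for this bleed only when planned treatment ends before Day 2 or is absent.

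**3. Size for one participant.** ABR = bleeds ÷ days in period × 365.25 (SAP 6.3.1.1). Efficacy period 2 starts on restart Day 169. At the minimum of 18 calendar months after restart, its length is 18 × 365.25 ÷ 12 − 168 ≈ 380 days.

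- One counted bleed adds 365.25 ÷ 380 = 0.96.
- If the period runs a further 30 days to the End of Study visit, it adds 365.25 ÷ 410 = 0.89.
- In one 6-month interval of treatment period 2, it adds 365.25 ÷ 182.625 = 2.0.
- Over an assumed 5 years on the original regimen (1826.25 days), it adds 365.25 ÷ 1826.25 = 0.20.

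**4. With the minimum added to event II.** The major window becomes the larger of its current end and 72 hours (72 hours if no treatment is given). The 48-hour bleed is then excluded after both classes in every row of the table.

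**The case against.** A fair defense has four parts.

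- **The treating dose may extend the window.** A bleed enters the primary ABR only if it is treated. If that dose counts as perioperative treatment, event II stretches over the bleed and removes it. Protocol Table 4 records completion of hemostatic coverage at SDay 2 to 14 or SDay 28, which fits this reading. Table 17 names extra, unplanned doses separately from planned ones, which fits the opposite reading. The SAP does not settle it, so the divergence is conditional. This part stands.
- **The difference may be deliberate.** Major surgery needs a written plan reviewed with the Medical Monitor where circumstances allow (Protocol 5.7). Minor surgery does not, so a fixed fallback is useful there. That explains why event III has a minimum. It does not explain why event II lacks one.
- **Few procedures are likely to be affected.** Protocol 5.7 recommends postponing non-urgent major surgery until after the trial, and antithrombotic treatment also lengthens the window. Short coverage is plausible, because Protocol 5.7 bases the plan on Section 5.3, which starts from a single dose with reassessment. That is inference; the documents give no count. This part stands.
- **Consequences are limited.** The primary objective is safety, the study is open-label with no powered test, and the effect runs against fitusiran. The treatment-policy ABR counts every treated bleed in surgery periods. This limits the importance of the point but does not make the on-treatment rule coherent.

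A reader might also infer that adding tooth implantation to the major class in Amendment 09 shifted the ABR during the study. The documents do not support that: the log records the addition as a clarification, and nothing shows that any procedure was reclassified.

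**Conclusion.** The inconsistency is real and lies in SAP 6.3, events II and III; Protocol 18.2.1 supplies only the split between classes. It changes a result only when planned treatment after a major procedure ends before the day of the bleed and the dose treating the bleed is not part of the plan. With no supplemental treatment, the major window cannot be programmed as written.

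The addition of about 0.96 to one participant's ABR in efficacy period 2 is close to a maximum, not a typical value. It assumes the minimum 18 months after restart, about 380 days, with no other exclusions and no early discontinuation. Participants continue to 72 months on study if that is later, and the addition falls as follow-up grows. It can exceed 0.96 only if discontinuation or other exclusions shorten the period.

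A reader might infer that the ABR as a whole is materially biased against fitusiran, or that every Day 2 bleed after a molar extraction counts. Neither follows. The number of affected procedures is not given, so the group effect cannot be computed; it is probably small. The point is still worth correcting because it touches the primary efficacy estimate and the correction is cheap.

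**What to change.** In SAP 6.3, event II, for surgery and for the bleeding endpoints only:

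1. End the window at the later of the final day of supplemental hemostatic or antithrombotic treatment and 72 hours from the end of surgery. Use 72 hours if no such treatment was given.
2. State whether factor or BPA given for a post-procedure bleed counts as part of the perioperative plan.

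Leave the major-surgery window used for the AE and laboratory tables (SAP 6.8.2 and 6.8.3) unchanged, so that the change removes no safety data from those tables.

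The cost is a short text change and a small programming change, with up to about 3 fewer person-days per major procedure. A few early post-surgical bleeds would leave the on-treatment estimate, which favors the drug, but they stay in the treatment-policy estimate. The bleeding endpoints would then use a different major-surgery window from the safety tables and from Protocol 5.7, so the SAP should say so. Major trauma, also in event II, is not covered by this change.

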18.3 DATA PROTECTION

All personal data collected and/or processed in relation to this study will be handled in compliance with all applicable Privacy & Data Protection laws and regulations, including the GDPR (General Data Protection Regulation). The study Sponsor is the Sanofi company responsible for ensuring compliance with this matter, when processing data from any individual who may be included in the Sanofi databases, including Investigators, nurses, experts, service providers, Ethics Committee members, etc.

When archiving or processing personal data pertaining to the Investigator and/or to the patients, the Sponsor takes all appropriate measures to safeguard and prevent access to this data by any unauthorized third party.

Protection of patient data

Data collected must be adequate, relevant and not excessive, in relation to the purposes for which they are collected. Each category of data must be properly justified and in line with the study objective.

"Patient race and ethnicity will be collected in this study because they are expected to modify the drug response/because they are required by regulatory agencies (eg, on African American population for the FDA or on Japanese population for the Pharmaceuticals and Medical Devices Agency in Japan)". They will not be collected in the countries where this is prohibited by local regulation.

- Patients will be assigned a unique identifier by the Sponsor. Any patient records or datasets that are transferred to the Sponsor or its service providers will be identifiable only by the unique identifier; patient names or any information which would make the patient identifiable will not be transferred to the Sponsor.
- The patient must be informed that his personal study-related data will be used by the Sponsor in accordance with applicable data protection laws. The level of disclosure must also be explained to the patient as described in the informed consent.
- The patient must be informed that his medical records may be examined by Clinical Quality Assurance auditors or other authorized personnel appointed by the Sponsor, by appropriate IRB/IEC members, and by inspectors from regulatory authorities.
- Patients must be informed that their study-related data will be used for the whole "drug development program", ie, for this trial as well as for the following steps necessary for the development of the investigational product, including to support negotiations with payers and publication of results.

Protection of data related to professionals involved in the study

• Personal data (eg, contact details, affiliation(s) details, job title and related professional information, role in the study, professional resume, training records) are necessary to allow Sanofi to manage involvement in the study and/or the related contractual or pre-contractual relationship. They may be communicated to any company of the Sanofi group ("Sanofi") or to Sanofi service providers, where needed.

- Personal data can be processed for other studies and projects. At any time, objection to processing can be made by contacting the Sanofi Data Protection Officer (link available at Sanofi.com).
- In case of refusal to the processing of personal data by or on behalf of Sanofi, it will be impossible to involve the professionals in any Sanofi study. In case the professionals have already been involved in a Sanofi study, they will not be able to object to the processing of their personal data as long as they are required to be processed by applicable regulations. The same rule applies in case the professionals are listed on a regulatory agency's disqualification list.
- Personal data can be communicated to the following recipients:
 - Personnel within Sanofi or partners or service providers involved in the study,
 - Judicial, administrative and regulatory authorities, in order to comply with legal or regulatory requirements and/or to respond to specific requests or orders in the framework of judicial or administrative procedures. Contact details and identity may also be published on public websites in the interest of scientific research transparency.
- Personal data may be transferred towards entities located outside the Economic European Area, in countries where the legislation does not necessarily offer the same level of data protection or in countries not recognized by the European Commission as offering an adequate level of protection. Those transfers are safeguarded by Sanofi in accordance with the requirement of European law including, notably:
 - The standard contractual clauses of the European Commission for transfers towards our partners and service providers,
 - Sanofi's Binding Corporate Rules for intra-group transfers.
- Professionals have the possibility to lodge a complaint with Sanofi leading Supervisory Authority, the "Commission Nationale de l'Informatique et des Libertés" (CNIL) or with any competent local regulatory authority.
- Personal data of professionals will be retained by Sanofi for up to thirty (30) years, unless further retention is required by applicable regulations.
- In order to facilitate the maintenance of Investigators personal data, especially if they contribute to studies sponsored by several pharmaceuticals companies, Sanofi participates in the Shared Investigator Platform (SIP) and in the TransCelerate Investigator Registry (IR) project (https://transceleratebiopharmainc.com/initiatives/investigator-registry/). Therefore, personal data will be securely shared by Sanofi with other pharmaceutical company members of the TransCelerate project. This sharing allows Investigators to keep their data up-to-date once for all across pharmaceutical companies participating in the project, with the right to object to the transfer of the data to the TransCelerate project.

Professionals have the right to request the access to and the rectification of their personal data, as well as their erasure (where applicable) by contacting the Sanofi Data Protection Officer: Sanofi DPO - [name] (to contact Sanofi by email, visit https://www.sanofi.com/en/our-responsibility/sanofi-global-privacy-policy/contact).

